**Lay Summary**

We propose a single-blinded, randomized-controlled, clinical trial to evaluate the impact of an innovative model of home-based palliative care on outcomes for patients with advanced dementia and their caregivers. 250 subjects (125 patients, 125 caregivers) will be enrolled from across the Mount Sinai Health System and randomized to receive the home-based palliative care program or usual care. Intervention patients will be cared for by a pyramid of palliative care focused providers, the core of which comprises specially trained community health workers, social workers, and registered nurses. These providers are supported by a palliative care advanced practice nurse and physician. All visits will be done by video or telephone from 3/19/20 due to the ongoing risk of transmission of COVID-19. Usual care patients will have the results of their baseline interview shared with their Mount Sinai provider. Additionally, caregivers in the usual care arm will receive training from a health coach on a health issue identified as important to them (e.g., smoking cessation, healthy eating). This is a kind of attention control. of this intervention on meaningful outcomes for patients, caregivers, and the health system. Outcomes are symptom control and quality of life in persons with dementia; caregiver burden; caregiver satisfaction with care; patient days in the hospital and ED visits. In exploratory analyses we will also determine if the intervention decreases costs of healthcare. Outcomes will be ascertained through interviews with caregivers, chart abstraction from the medical record, and the Mount Sinai Data Warehouse.

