#### **Objectives**

The objective of this study is to determine whether a new home based palliative care program for patients with advanced dementia: 1) Improves overall symptom control and quality of life in patients with dementia; 2) Reduces caregiver burden, increases caregiver satisfaction, reduces caregiver depression; and 3) Reduces healthcare utilization (number of hospital admissions, days in hospital, emergency department visits) and increases days at home.

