### **Procedures for Investigator to Withdraw Subjects**

1. Death of patient (caregiver will be withdrawn)
2. No available caregiver
3. Transition to long term care (patients and caregivers)
4. Transition to skilled nursing facility for longer than 30 days (patients and caregivers)
5. Inpatient hospitalization for longer than 30 days (patients and caregivers)
6. Relocation of patient outside of Manhattan
7. Safety of clinical team cannot be assured
8. Study stopped
9. Principal Investigator deems it to be in the subject's best interest
10. The subject withdraws permission to use their PHI for research

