## Statistical Analysis Plan

ID: GCO 17-02787

Palliative Care at Home for Dementia

NCT03798327

[name] – PI

March 2020

**1. Overview.** For continuous outcomes, we will compare the changes from baseline across multiple repeated measurement points between different treatment groups using mixed linear model to control for within-subject effect.

**2. Descriptive Study.** We will characterize subjects with regard to baseline and follow-up measures and change between assessments. Descriptive statistics of demographics, disease-related and treatment related variables will be calculated and compared at baseline between the treatment group and control group. T-test, Chi-square, Fishers exact test will be used as appropriate.

**3. For the primary outcomes measures,** we will examine changes in outcomes over time. As possible, we will test the differences in mean total scores between the main predictors of treatment groups (intervention vs. control) and time (baseline, 3 months, and 6 months), and the interaction term between these two predictors, which indicates the variation of difference of outcome trajectories between interventions and controls by baseline scores.

**4. Utilization.** We will measure counts of utilization including, as applicable, those related to the number of hospital admissions, number of hospital days, number of days out of hospital, and ED usage. We will perform simple counts followed by descriptive statistics between the two groups.

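### SAP section 4 answers the comparative utilization objective with arm-wise descriptives only: no between-arm estimate or interval, no allowance for followed time or death, and days out of hospital in place of days at home

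*SAP*

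**What the plan says.** Protocol section 3 (Objectives) sets out to determine whether the program: "Reduces healthcare utilization (number of hospital admissions, days in hospital, emergency department visits) and increases days at home". The endpoint list in the same section puts utilization in its third group, after the co-primary symptom and quality-of-life scales. The Lay Summary names hospital days and ED visits among the outcomes and sets only cost apart: "In exploratory analyses we will also determine if the intervention decreases costs of healthcare".

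SAP section 4 lists admissions, "number of hospital days, number of days out of hospital, and ED usage", and gives the whole method in one sentence: "We will perform simple counts followed by descriptive statistics between the two groups".

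No other SAP section supplies more for utilization:
- Section 1 reads "For continuous outcomes, we will compare the changes from baseline across multiple repeated measurement points between different treatment groups using mixed linear model", which concerns change scores at repeated visits.
- Section 2 attaches its tests to the baseline comparison.
- Section 3 covers the primary outcomes.

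Protocol section 9 withdraws patients for, among other reasons, death, long-term care, a skilled nursing facility (SNF) or hospital stay beyond 30 days, and a move out of Manhattan. When the subject or representative asks to withdraw, permission is sought to keep collecting routine-care information. Section 20 plans extraction of enrolled patients' encounters up to study termination. Section 23 refers the reader to a data analysis plan in an accompanying proposal.

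**The concern.** The objective is a directional comparison between arms, and the method stops at describing each arm. Three things follow.

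1. Raw counts depend on how long each patient is followed. If the arms differ in the number or timing of exits, counts differ even when the underlying rates are equal. One exit, a hospital stay beyond 30 days, is triggered by an outcome that SAP section 4 counts. If counting stops at exit, that outcome cuts short its own measurement.
2. Days out of hospital is not days at home. An SNF stay of up to 30 days does not trigger exit; it is time out of hospital but not at home. Days after death have no rule, in a population for whom Protocol section 10 calls death an expected outcome. If post-death days are credited, the arm with more deaths looks better.
3. Without intervals, a reader cannot see how imprecise the comparison is at this sample size, and may over-read a difference or its absence.

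**Working it through.** **Inputs from the documents.** The Lay Summary states that "250 subjects (125 patients, 125 caregivers) will be enrolled". Allocation is 1:1 (Protocol section 12), so about 62 patients per arm. Follow-up is 6 months (section 3), taken here as 180 days. The plan gives no figure for utilization to reproduce, and no event, death or exit rate or SD. Every rate below is therefore an assumption.

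**Step 1: objective against SAP section 4.**

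| Objective | SAP section 4 | Between-arm estimate or interval | Rule for death or exit |
|---|---|---|---|
| Hospital admissions | listed | none | none |
| Days in hospital | listed | none | none |
| ED visits | listed | none | none |
| Days at home | not listed; days out of hospital instead | none | none |

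**Step 2: raw counts when the true rates are equal.** If a share p exits by 6 months at a constant hazard unrelated to use, the mean followed fraction is p / (−ln(1−p)): 0.9748 for 5%, 0.9491 for 10%, 0.9230 for 15%, 0.8963 for 20%, 0.8411 for 30%. Ratios are intervention over control.
- 30% v 20% exit: 0.8411 / 0.8963 = 0.94.
- 10% v 30% exit: 0.9491 / 0.8411 = 1.13.
- 20% in both arms, at month 1 v month 5: (1 − 0.2×5/6) / (1 − 0.2×1/6) = 0.8333 / 0.9667 = 0.86.
- If records are counted to death or 6 months and half of exits are deaths, the first two become 0.9230 / 0.9491 = 0.97 and 0.9748 / 0.9230 = 1.06.

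**Step 3: effect of the day-counting rules.**
- A 60-day hospital stay cut at day 30 lowers its arm's mean by (60 − 30) / 62 = 0.48 days.
- A survivor with a 30-day SNF stay and no hospital stay scores 180 days out of hospital but 180 − 30 = 150 at home.
- A death on day 30 with no hospital stay scores 30 or 180 according to the rule, moving the arm mean by (180 − 30) / 62 = 2.4 days.
- Deaths of 15% v 10%: the choice of death rule moves the between-arm difference by 180 × (0.9491 − 0.9230) = 4.7 days. Deaths of 5% v 15%: 180 × (0.9748 − 0.9230) = 9.3 days.

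**Step 4: precision at 62 per arm.**
- Admissions. The 95% interval is the estimate multiplied and divided by exp(1.96 × √[2(1/(0.87m) + k)/62]). Here m is 0.5 to 1.5 admissions per 6 months, k is a negative binomial dispersion of 0.5 to 1.0, and 0.87 is the average of the followed fractions 0.8411 and 0.8963. The factor runs from 1.49 to 1.90.
- Hospital days. The factor is exp(1.96 × √[2CV²/62]): 2.02 if the SD is twice the mean, 2.88 if three times.
- Days at home. The half-width is 1.96 × SD × √(2/62): 10.6 days for an SD of 30, 21.1 for an SD of 60.

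The distortions in step 2 amount to a factor of at most 1/0.86 = 1.16, inside even the narrowest interval factor of 1.49. The death-rule shifts of 4.7 and 9.3 days are below the narrower half-width of 10.6.

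**The case against.** The strongest reply is that this is a pilot (Protocol section 24) and only the symptom and quality-of-life scales are co-primary, so describing utilization by arm is a reasonable choice. That stands as a reason not to test. It does not excuse leaving out an estimate, because the objective is worded as a comparison. Published means, SDs and numbers would let a reader build a crude difference and a crude interval, but not one adjusted for followed time or prior use, and not one with a known rule for death.

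The SAP's list is also open-ended, and days at home appears in the objective but not in the endpoint list. So the mismatch may be a definition to reconcile rather than a deliberate substitution. It still needs reconciling.

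The numbers are small and rest on assumed rates. The 1.13 and 9.3-day cases need a threefold difference in exits or deaths between arms, for which the documents give no basis. That stands, and it limits the weight of the point.

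Two stronger readings are tempting, and the documents do not support either:
- *No comparative analysis of utilization was ever planned.* Protocol section 23 points to an analysis plan in a proposal that was not supplied. Only the SAP and protocol text can be judged.
- *Data stop at withdrawal.* Section 9 provides for records after a requested withdrawal, with permission. Section 20's extraction names no stop at exit, although study termination is not defined there. Section 9 also lists loss of permission to use health information as a separate exit, which suggests that the other exits need not end record access. The consent text was not available to settle this. What is absent is the analysis rule.

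**Conclusion.** The point holds for the SAP as supplied. A non-primary but comparative objective has no between-arm estimate, no interval and no rule for followed time or death, and one of its four outcomes is replaced by a measure that differs for SNF days and, depending on the rule, for days after death.

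Under the assumed rates, the distortions are raw-count ratios of about 0.86 to 1.13 with no true difference, and death-rule shifts of about 5 to 9 days. Both are modest beside the intervals expected at about 62 per arm. It would therefore go too far to infer that the omission would by itself overturn the trial's utilization result. The main losses are that the stated question is not answered as posed and that its imprecision is not shown. The primary endpoints are unaffected. The point should be fixed before arm-level data are seen.

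**What to change.** In SAP section 4:

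1. **Window.** Count events from randomization to 6 months or death, using encounter dates.
2. **Estimates.** Report between-arm rate ratios with 95% intervals for admissions, ED visits and hospital days. Use a count model allowing overdispersion for admissions and ED visits. For hospital days, which cluster within stays, use a log-link mean model with a robust or bootstrap interval.
3. **Followed time.** Use as offset the log of days alive and observable in the records. End observable time at relocation, or wherever record use is not permitted, unless claims data cover the later period. Otherwise a patient who moves away adds exposure while outside events go unseen.
4. **Prior use.** Adjust for the previous 12 months: admissions and ED visits from the baseline chart field in Protocol section 20, hospital days from the admit and discharge dates in the encounter extract. The extract must reach back far enough before randomization.
5. **Deaths and exits.** Show them by arm and reason beside the utilization results.
6. **Days at home.** Add days alive and at home as a between-arm mean difference with a 95% interval. Days after death, in hospital, in an SNF or in long-term care do not count as home.
7. **Reporting.** State that all events and facility days outside Mount Sinai may be incompletely captured, and present the results as pilot estimates, not tests.

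If the separate proposal already contains such rules, carry them into the SAP.

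**Cost.** Mostly wording and a little more analysis. For admissions, ED visits and hospital days at Mount Sinai the data are already planned: encounter dates and prior-use counts (section 20), and chart abstraction after each hospitalization (section 12). Consent must be checked for record use after an investigator withdrawal. If it does not permit this, counting stops at exit and the SAP should say so, or IRB action is needed. Days at home is harder, because facility dates outside the system will be incomplete. The intervals will be wide.

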**Description of Health Information That Will Be Viewed, Recorded, or Generated**

Data warehouse query (screening purposes):

1. Patient name
2. Patient MRN
3. All encounters within the Mount Sinai system in quarter of request and 12 months prior:
  - a. Encounter ID
  - b. Dates of encounter (admit and discharge)
  - c. Encounter type (e.g., outpatient, inpatient)
  - d. Discharge disposition
  - e. Discharge location to
  - f. ICD10 code and diagnosis description
  - g. ICU admission
  - h. Encounter site
  - i. Provider
  - j. Payer
  - k. Wheelchair order
  - l. Hospital bed order
4. Patient zipcode
5. Patient date of birth

From this information, we will generate a list of patients with a diagnosis of dementia. We will then review the charts of these patients to determine potential eligibility.

Chart review (screening purposes):

1. Name, MRN, date of birth
2. Physician note of behavioral or psychological symptoms of dementia (yes/no)
3. Psychotropic medication (yes/no; type)
4. Documented MMSE < 20 in past 6 months (yes/no).
5. Evidence of any of the following: needs assistance with dressing, bathing, toileting; urinary or fecal incontinence; weight loss; dysphagia/ aspiration; immobility; loss of ability to communicate (yes/no; checkbox for each)

Interviews (enrolled subjects):

Patients:

Demographics (study team)  
Symptoms (SM-EOLD) - standardized  
Quality of life (QOL-AD) - standardized  
Function (KATZ ADL and IADL) - standardized  
Resource use (RUI) - standardized  
Care preferences - study team  
Cohen Mansfield Agitation Inventory - standardized  
Financial burden - study team  
Neuropsychiatric Inventory Questionnaire - standardized

Caregivers:

Caregiver demographics (study team)  
Caregiver burden (Zarit Burden Inventory) - standardized  
Caregiver depression (PHQ-9) - standardized  
Caregiver satisfaction with care (FAMCARE-10) - standardized  
Caregiver self efficacy (revised scale for caregiving self-efficacy) - standardized  
Caregiver comorbidities (KATZ) - standardized

Chart reviews at baseline and follow up (enrolled subjects)

1. Medications (name, dose)
2. Hospitalizations and ED visits in past 12 months (yes/ no/ number)
3. Advance care planning documentation
4. Receipt of any of the following: (i) IV fluids (ii) IV antibiotics (iii) PEG (iv) Intubation (v) CPR

Data warehouse (enrolled subjects):

All encounters in the Sinai health system from enrollment until study termination:

1. Patient name
2. Patient MRN

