3. All encounters within the Mount Sinai system in quarter of request and 12 months prior:
  - a. Encounter ID
  - b. Dates of encounter (admit and discharge)
  - c. Encounter type (e.g., outpatient, inpatient)
  - d. Discharge disposition
  - e. Discharge location to
  - f. ICD10 code and diagnosis description
  - g. ICU admission
  - h. Encounter site
  - i. Provider
  - j. Payer
  - k. Wheelchair order
  - l. Hospital bed order
4. Patient zipcode
5. Patient date of birth
6. Costs associated with care

**Non-Health Related Information Will Yes  
Be Viewed or Recorded**

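### SAP section 4 compares utilization by arm without the prior-year admission and ED counts taken at baseline, giving up precision that would cost almost nothing to gain

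*SAP*

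**What the plan says.** Utilization is the third study aim. Protocol section 3 (Objectives) asks whether the program "Reduces healthcare utilization (number of hospital admissions, days in hospital, emergency department visits) and increases days at home". SAP section 4 names the measures as "the number of hospital admissions, number of hospital days, number of days out of hospital, and ED usage", and the whole of its analysis is "We will perform simple counts followed by descriptive statistics between the two groups". It names no covariate, change score, model or interval.

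The baseline information exists. Protocol section 20, under "Chart reviews at baseline and follow up (enrolled subjects"), lists "Hospitalizations and ED visits in past 12 months (yes/ no/ number"). The same section requests warehouse data on enrolled patients, with admit and discharge dates, described as "All encounters within the Mount Sinai system in quarter of request and 12 months prior".

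No other part of the plan brings prior use into the comparison:

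- SAP section 1 limits its mixed model: "For continuous outcomes, we will compare the changes from baseline across multiple repeated measurement points between different treatment groups".
- SAP section 2 is a balance check. Its variables "will be calculated and compared at baseline between the treatment group and control group", with no adjustment.
- SAP section 3 concerns the primary outcome scores.
- Protocol section 12 gives 1:1 allocation and mentions no stratification by prior use.

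**The concern.** Patients who were often in hospital last year tend to be in hospital more this year. With 125 patients in two arms, a modest surplus of frequent users in one arm is an ordinary chance event. A comparison of follow-up counts alone cannot separate that surplus from an effect of the program. Because SAP section 4 plans no interval, a reader would not see how large the chance error is either.

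A covariate that predicts the outcome, is measured before treatment and is already being abstracted would reduce both problems. At stake is the sharpness of the answer to the third objective. The co-primary endpoints are not affected.

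**Working it through.** The plan states no rate, dispersion, correlation or power figure for utilization, so there is no figure of its own to reproduce. Protocol section 23 refers the power and data analysis plan to an accompanying proposal, which is not among the documents.

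**Inputs from the documents.** 125 patients (Protocol, Lay Summary), allocated 1:1 (section 12), so 63 and 62 per arm; 6 months of follow-up (section 3); a 12-month look-back (section 20).

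**Step 1: gain for an assumed correlation.** With r the correlation between prior-year and follow-up counts, linear adjustment multiplies the variance of the arm difference by 1 − r² and the interval width by √(1 − r²).

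- r = 0.3: 1 − 0.09 = 0.91, a 9% cut; √0.91 = 0.954, interval about 5% narrower.
- r = 0.5: 1 − 0.25 = 0.75, a 25% cut; √0.75 = 0.866, interval about 13% narrower.

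A baseline imbalance of 1 SE moves the expected raw follow-up difference by r SE, here 0.3 to 0.5 of its standard error.

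**Step 2: which correlations are plausible?** Assume a gamma-Poisson (negative binomial) model. A patient-level frailty with variance v drives a follow-up count with mean μ over 6 months and a prior count with mean 2μ over 12 months. Then

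- Var(follow-up) = μ + vμ²
- Var(prior) = 2μ + 4vμ²
- Cov = 2vμ² if frailty is fully stable, and half that in a less favourable case.

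All values of μ and v below are assumptions. Worked case, μ = 0.5 and v = 1: variances 0.75 and 2, covariance 0.5, so r = 0.5/√1.5 = 0.41. The raw standard error is √(0.75 × (1/62 + 1/63)) = 0.155 admissions per patient, 31% of the mean. Adjustment multiplies it by √(1 − 0.167) = 0.91.

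| μ | v | r, stable | SE factor | r, half covariance | SE factor |
|---|---|---|---|---|---|
| 0.3 | 0.5 | 0.17 | 0.98 | 0.09 | 1.00 |
| 0.5 | 1 | 0.41 | 0.91 | 0.20 | 0.98 |
| 1.0 | 1 | 0.58 | 0.82 | 0.29 | 0.96 |
| 1.0 | 2 | 0.73 | 0.68 | 0.37 | 0.93 |

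Over the full grid (μ 0.3 to 1.0, v 0.5 to 2), the factor is 0.68 to 0.98 with stable frailty and 0.93 to 1.00 with half the covariance.

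**Step 3: simulation with no true effect.** 2,000 replicates per scenario, five scenarios, stable frailty.

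- The raw difference averaged about zero in every scenario, so it is unbiased over randomizations.
- In the central case (μ = 0.5, v = 1), the SD of the difference fell from 0.153 to 0.138 with linear adjustment. On the log rate-ratio scale, a Poisson model with the log prior count took it from 0.314 to 0.288, a factor of 0.92.
- Among replicates where one arm exceeded the other in prior use by more than 1 SD, the average spurious difference was 13% to 33% of the mean unadjusted and within about 4% adjusted.

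**The case against.** The strongest reply is that SAP section 4 is descriptive. It plans no test, interval or p-value, so there is no estimate to adjust. Protocol section 24 calls the trial a pilot, and the co-primary endpoints are symptoms and quality of life. On this view, adjusting a non-primary outcome is an efficiency choice, and leaving it out is not an error. That last part stands and sets the weight of the point. It does not remove the gain, because section 4 is the only plan supplied for answering a comparative objective. The unseen proposal might contain a model; the current SAP does not.

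Three stronger readings are tempting, and the documents do not support them.

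- A reader might infer that baseline imbalance passes undiminished into the result, or that the raw comparison is biased. Allocation is random, so it is unbiased over repetitions, and only the fraction of an imbalance given by the correlation carries over.
- A reader might take the frequency of imbalance as the size of the problem. With mean 1 and dispersion 1 assumed, the SD is √2 = 1.414 and the standard error is 1.414 × √(2/62) = 0.254. An imbalance above 0.25 then has probability of about 0.325. But that threshold is almost exactly 1 SE, so the figure describes any baseline variable and says nothing about error in the outcome.
- A reader might suppose that the counts are known to be heavy-tailed. The documents give no distribution; skew is a reasonable assumption only.

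One practical objection also stands. The chart item covers admissions and ED visits, not prior hospital days, so a ready-made covariate exists for only some of the measures.

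**Conclusion.** The point holds as a low-cost improvement. Prior-year admissions and ED visits are collected at baseline, and the utilization comparison ignores them. The cost is lost precision and, in the single allocation actually drawn, exposure to chance imbalance in proportion to the correlation.

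If that correlation is 0.3 to 0.5, the variance falls by about 9% to 25% and the interval narrows by about 5% to 13%. If use is rare or last year's use is a poor guide to the next six months, the gain is near nil. Rates, frailty and correlation are all assumed, so the range matters more than any single value in it. The point is separate from the absence of a count model: adding a model without the prior-year count would leave this gap open.

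**What to change.** In SAP section 4, before outcomes are examined by arm:

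- **Admissions and ED visits.** Fit a negative binomial or similar count model with treatment arm, log time observed as offset, and log(1 + the same patient's prior-12-month count) as covariate. Take the covariate from the baseline chart review. Report the adjusted rate ratio with 95% CI beside the raw counts.
- **Hospital days.** Use prior-year admissions as the covariate, or prior days derived from warehouse admit and discharge dates. If the latter, state the limits: Mount Sinai encounters only, and a look-back tied to the quarter of the data request and not to enrollment.
- **Days out of hospital.** This can stay descriptive, since it depends on hospital days and time observed.
- **Offset.** Define when time observed ends for patients who die or are withdrawn under Protocol section 9.

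The cost is a few sentences in the SAP, slightly more analysis work and a model assumption for a non-primary outcome. Admissions and ED visits need no new data collection; prior hospital days need a derivation from data already requested. The raw counts remain in the report, so nothing now planned is lost.
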